Researchers will also discuss the study with the person themselves in a way appropriate to their level of understanding. If there is any indication that the individual does not agree with any part of the study, the individual will not take part even if their participation has been advised by another person on their behalf. If this occurs, researchers will inform the individual's consultee that the individual will not be taking part, despite their advice and will explain the reasons for this. There is clear potential for the research to benefit individuals with cognitive impairment and the study methods (interviews and observations) pose minimal risk to participants. All data collection will be completed with sensitivity and respect for the autonomy and privacy of each participant.

The following safeguards will apply once an individual has been recruited in this way:

- No actions will be taken during any part of the study if the participant seems to object to it (unless the action is vital to protect the individual from harm).
- Researchers will consider the interests of the participant above all else throughout the study.
- The participant will be withdrawn if any conditions pertaining to his or her inclusion in the project no longer apply and/or if he or she gives any indication of not wanting to continue or take part.

The consent form for all individuals will include an option to indicate a preference for or against continued participation, should the individual lose the capacity to consent during the study.

Measures

6-CIT (Brooke & Bullock, 1999)

The 6CIT is a short screening measure for dementia. It is administered in around 3-4 minutes and asks questions about the current time, month and year, as well as testing the participant's ability to recall a five-component address and list the numbers 1-20 and the months of the year in reverse. Permission to use the measure has been obtained from the authors.

MoCA (Nasreddine et al., 2005)

The MoCA was designed as a rapid screening instrument for mild cognitive dysfunction. Different cognitive domains (including attention, memory, visuo-spatial skills and orientation) are assessed using a series of short tests. The time taken to administer the MoCA is approximately 10 minutes. The total possible score is 30 points with a score of 26 or above considered normal. Permission is required to use the MoCA for research purposes and it has already been granted in regard to this study.

iii. Data Analysis

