The principal approach will be to examine the capacity of the 6CIT to detect cognitive impairment including dementia at different recognised levels. The approach employed in these analyses would be the measurement of agreement between categories using Kappa (e.g. Cohen, 1960; Fleiss, 1975; Kraemer, 1992). We will also examine the relationship between the items and combinations of items on the scales, and with this ordered data, will employ weighted kappa as the measure of agreement (Cohen, 1968; Dunn, 1989). This will establish whether the 6CIT has suitable psychometric properties to be used as a routine screen in prisons. We will estimate the prevalence of cognitive impairment by calculating percentages and 95% confidence intervals (CIs) using the 6CIT, for comparison with prevalence estimates based on the MOCA. We will estimate the sensitivity, specificity, false positive rate and false negative rate for 6CIT, using the MOCA as a robust, validated measure. From the MoCA and ACE-III score stratification into mild, moderate and severe, we will select individuals for further interview in Part 3 and create the vignettes in Part 4.

b. Stage Two - Full needs assessment

i. Sample

Those who screen positive on the MoCA in stage one and consent to a further interview, will be invited to meet again with researchers.

ii. Procedure

The full needs assessment interview may take place immediately after the part one interview or may be delayed by a short time, depending on the operational arrangements at each study site and the individual's preference or needs. A further, fairly lengthy interview may be difficult and distressing for individuals with cognitive impairment, so researchers will consider the needs and wishes of each participant prior to continuing with stage two. If it is operationally a viable option and the individual is able and willing to continue with a full needs assessment, then both interviews may be conducted at the same appointment. If this is not the case, the researcher will arrange a new appointment via the research nurse and will return to complete the full needs assessment at a different time. As far as possible, the time between interviews will be kept at a minimum, to maximise the validity of results

(as individuals with cognitive impairments may fluctuate in their cognitive ability and lucidity from day to day and/or their abilities may deteriorate over even short periods of time).

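### The conclusion that the 6CIT suits routine prison use is tied to kappa, although the sensitivity and specificity that answer the question are already planned

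*Protocol*

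**What the plan says.** The relevant text is the Data Analysis paragraph of the Protocol, Section 4 (Study Part One), Stage One. In order, it says:

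- The aim is detection: "The principal approach will be to examine the capacity of the 6CIT to detect cognitive impairment including dementia at different recognised levels".
- The method for that aim is kappa: "The approach employed in these analyses would be the measurement of agreement between categories using Kappa".
- For items and combinations of items, the authors "with this ordered data, will employ weighted kappa as the measure of agreement".
- The conclusion follows directly: "This will establish whether the 6CIT has suitable psychometric properties to be used as a routine screen in prisons".
- After a sentence on prevalence estimates, accuracy is added: "We will estimate the sensitivity, specificity, false positive rate and false negative rate for 6CIT, using the MOCA as a robust, validated measure".

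The Measures subsection gives the two tests different targets: "The 6CIT is a short screening measure for dementia" and "The MoCA was designed as a rapid screening instrument for mild cognitive dysfunction". For the MoCA it adds "The total possible score is 30 points with a score of 26 or above considered normal". It gives no 6CIT cut-off. Nowhere does the protocol set a target or threshold for kappa, sensitivity or specificity.

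**The concern.** Validating the 6CIT is the second study objective. As the paragraph is built, the sentence that delivers the verdict refers back to kappa and weighted kappa, not to the accuracy measures that come after it.

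Kappa suits two raters who assign the same categories and have equal standing. Here the 6CIT is the test being judged and the MoCA is the reference. Three properties of kappa then matter:

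- It is a single number, so it does not show whether disagreement comes from impaired prisoners missed or from unimpaired prisoners flagged. For a screen meant to find people early, these errors differ in consequence.
- At unchanged sensitivity and specificity it changes with prevalence. The Sampling Procedure aims for half the sample to be aged 70 or over and notes that prevalence doubles with every five years of age, so sample prevalence is partly a product of design. The quota may also be revised after the recruitment pause.
- It falls when the two tests flag different proportions. That is plausible given their different targets.

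At stake is whether the recommendation on routine use follows from how well the 6CIT finds impaired prisoners, or from an index that also reflects who was sampled.

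**Working it through.** **Inputs.** The protocol gives no figure for kappa, sensitivity or specificity, so there is none to reproduce. Its one usable number is the 7% prevalence behind the sample size (Section 4, Sample). That figure comes from Mini Mental State Examination results in a study of older male prisoners in North-West England (Section 3), not from the MoCA. All sensitivities, specificities and other prevalences below are assumptions, so a range is shown.

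**Formula.** With prevalence p, sensitivity Se and specificity Sp:

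- observed agreement Po = p·Se + (1−p)·Sp
- index-positive rate q = p·Se + (1−p)·(1−Sp)
- chance agreement Pe = q·p + (1−q)·(1−p)
- kappa = (Po − Pe)/(1 − Pe)

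**Step 1: two screens at p = 0.07.**

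- Screen A, Se 0.90, Sp 0.90: Po = 0.063 + 0.837 = 0.900; q = 0.063 + 0.093 = 0.156; Pe = 0.0109 + 0.7849 = 0.7958; kappa = 0.1042/0.2042 = 0.51.
- Screen B, Se 0.50, Sp 1.00: Po = 0.035 + 0.930 = 0.965; q = 0.035; Pe = 0.00245 + 0.89745 = 0.8999; kappa = 0.0651/0.1001 = 0.65.

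Per 1,000 people, 70 are impaired. A misses 7 and B misses 35. A raises 93 false alarms and B none. Kappa ranks B higher.

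**Step 2: the same screens across prevalence.**

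| Prevalence | A (0.90/0.90) | B (0.50/1.00) |
|---|---|---|
| 2% | 0.24 | 0.66 |
| 7% | 0.51 | 0.65 |
| 15% | 0.67 | 0.63 |
| 30% | 0.77 | 0.58 |
| 50% | 0.80 | 0.50 |

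For A, kappa reduces to 1.6p(1−p)/[0.1 + 1.6p(1−p)]; for B, to (1−p)/(1.5−p). Setting them equal gives 0.8p = 0.1, so p = 12.5%. B outranks A only below that prevalence. The drift of A with prevalence holds across the whole range.

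**Step 3: effect of the age quota.** In Section 3, 3,720 of 11,980 men over 50 were over 60 (31%), so the share aged 70 or over cannot exceed 31%, against 50% in the target sample. As an illustration, assume 4% impaired below 70, 16% at 70 or over, and 10% of the population aged 70 or over:

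- population prevalence = 0.9 × 0.04 + 0.1 × 0.16 = 5.2%
- sample prevalence = 0.5 × 0.04 + 0.5 × 0.16 = 10%
- kappa for screen A = 0.44 and 0.59 respectively

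**Step 4: unequal positive rates.** Suppose 7% are MoCA-positive and 25% are 6CIT-positive, with every MoCA-positive person among them. Then Se = 1.00 and Sp = 0.75/0.93 = 0.81. Po = 0.82, Pe = 0.0175 + 0.6975 = 0.715, and kappa = 0.105/0.285 = 0.37, although the 6CIT misses nobody.

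**The case against.** The strongest reply is that the right quantities are already in the plan. Sensitivity, specificity and both error rates against the MoCA will be reported beside kappa, as will prevalence by each test, so a reader will see a mismatch in positive rates. The paragraph opens with detection, and its reference to several recognised levels suggests more than one cut-off. The sentence on suitability can be read loosely as covering the whole analysis. All of this stands, and it limits the point to which statistic carries the conclusion.

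Some stronger readings are tempting but not supported:

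- **That the plan would reject a good screen.** It has no kappa threshold and no accept-or-reject rule. Moreover, if the 6CIT flags far fewer people than the MoCA, sensitivity is low too. At 7% against 30% positive with full nesting, sensitivity is 0.07/0.30 = 23%, and a low kappa is then a fair signal for that cut-off.
- **That kappa ignores accuracy.** It is a function of sensitivity, specificity and prevalence; the difficulty is the mixing.
- **That unlike 6CIT and MoCA items will be cross-tabulated for weighted kappa.** The sentence speaks of items on the scales and does not say which are paired.
- **That further accuracy analyses are missing.** Predictive values and optimism correction for a chosen cut-off may sit in a statistical analysis plan that is not at hand.

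It is also fair to say that the age quota alters case mix, which can shift sensitivity and specificity. They do not, however, change mechanically with prevalence as kappa does.

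**Conclusion.** The point holds as a matter of emphasis that is cheap to correct. The protocol names kappa as its approach to a detection question and attaches the suitability conclusion to it, while the measures that answer the question are planned but unlinked to that conclusion.

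The size depends on assumed accuracies. At 7% prevalence, kappa favours a screen that misses half of cases over one that finds 90% (0.65 against 0.51). This reversal disappears above 12.5% prevalence, and the MoCA-positive rate may well exceed that. The dependence on prevalence at unchanged accuracy (0.51 at 7%, 0.77 at 30%) does not need low prevalence. No planned estimate is invalid, and the sample size is unaffected.

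**What to change.** Reword the Data Analysis paragraph of Part One, Stage One so that:

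1. The suitability conclusion rests on the sensitivity and specificity already planned, with 95% CIs, at the recognised 6CIT cut-off or cut-offs, which should be stated.
2. The ROC area of the 6CIT total score against a MoCA score below 26 supports it.
3. Kappa and weighted kappa remain as secondary descriptions, reported with the positive rate on each test.

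The cost is a change of wording and a little extra analysis. Both tests are already given to every participant, so no new data or participants are needed.

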We will aim to recruit at least860 prisoners aged 50 and over, including 269 women and 591 men. Within each sex, this sample size will allow the estimation of a prevalence of 7% (based on Hayes et al., 2012) with 2% precision (95% confidence intervals (CIs) 5% to 9%, applying finite sample corrections for each sex).

Sampling Procedure

We have developed our sampling procedure based on a review of the existing literature.

The sample will be drawn randomly from all female prisons and a representative range of adult male prisons across England and Wales, including local prisons holding those on remand, serving short sentences and in the early part of long sentences; training and dispersal prisons holding men part-way

through long sentences; high secure establishments holding those considered to be high risk; and open prisons holding short term prisoners deemed low risk and those in the final stages of long sentences, who are preparing for community release.

We have selected sites based on the proportion of each prison type in the prison estate as a whole-1 of the 8 high secure sites; 3 of the 31 locals; 5 of 51 category B or C training and dispersal prisons and 1 of the 7 category D/open prisons (as defined by the justice.gov.uk prison index – accessed 9th May 2016). We will also include a prison that has a specific wing for older and disabled prisoners. This is one of only two prisons in the country with a dedicated wing for prisoners based on their age and health needs. However, other prisons do have a large number of older prisoners as a result of them housing vulnerable prisoners (i.e. prisoners who are considered at risk from other prisoners, often due to their age or the nature of their offence).

We estimate that we will need to initially approach approximately 415 females and 896 males to allow for 20% refusing to participate and a further 14% who may be unavailable on the day; unable to consent; or have already been interviewed for the study in a previous establishment. (These estimates are based on Hayes et al. 2012 study, in which researchers conducted a one-day census of all prisons in North-West England and interviewed all males aged 60+ resident in each establishment).

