We will establish the total number of prisoners aged 50+ in the recruiting prisons and use these figures to calculate a sampling fraction, which will inform the proportion of prisoners we will approach at each site. For example, if there are a total of 1500 males aged 50+ in the prisons we approach, we will sample 60% of older prisoners at each site(896/1500). We will also stratify our sample according to age, an important variable when investigating cognitive impairment, as prevalence doubles with every increase of five years (Jorm & Jolley, 1998). We will therefore aim for half of our overall sample (for males and females) to be aged 50-69 years and half to be aged 70+.

We will review the recruited sample at regular intervals, pausing recruitment briefly (initially after we have recruited one quarter of the sample) and reviewing the sampling strategy, to consider, for example, whether we need to recruit a greater proportion of a particular age group. The first phase of recruitment (after one quarter are recruited) will effectively act as a pilot for the remainder.

Inclusion/Exclusion criteria

Anticipated inclusion criteria:

- i) Aged 50 or over;
- ii) Resident in one of the participating prison establishments on the day of the census.

Anticipated exclusion criteria:

- i) Considered by prison or healthcare staff not safe to interview alone due to their current risk assessment;
- ii) Previous inclusion in the study;
- iii) Does not have a functional command of the English language.
- iv) Lacking the capacity to provide informed consent AND an appropriate Personal or Independent Consultee cannot be identified/contacted, is unwilling to be consulted or makes the decision to refuse consent.

Participants will only be included if they can speak and understand English to a sufficient level and researchers are satisfied that their English language ability will not adversely impact their test scores. There are significant language biases in some tests, which cannot be overcome by straightforward translation or use of an interpreter. Some tests are available in other language

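### The conclusion that the 6CIT suits routine screening is tied to kappa, which moves with the age mix set by the sampling, and not to the sensitivity and specificity already planned

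*Protocol*

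**What the plan says.** Objective 2 of the protocol (section 2) is to validate the 6CIT for prisoners aged 50 and over. Section 4 gives the purpose as early and consistent identification of possible impairment.

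The analysis is in section 4, Stage One, iii. Data Analysis. It opens with a detection aim: "The principal approach will be to examine the capacity of the 6CIT to detect cognitive impairment including dementia at different recognised levels". The next sentence names the method: "The approach employed in these analyses would be the measurement of agreement between categories using Kappa". Weighted kappa is then added for items and combinations of items. The paragraph goes on: "This will establish whether the 6CIT has suitable psychometric properties to be used as a routine screen in prisons".

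After a sentence on prevalence comes: "We will estimate the sensitivity, specificity, false positive rate and false negative rate for 6CIT, using the MOCA as a robust, validated measure". No criterion or conclusion is attached to these estimates. No threshold or adequacy level is given for any measure, kappa included.

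Under Sampling Procedure in the same Stage, the protocol aims for "half of our overall sample (for males and females) to be aged 50-69 years and half to be aged 70" or over. It gives as the reason that prevalence doubles with every five years of age. It also allows the age mix to be adjusted when recruitment is reviewed.

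**The concern.** Whether a screen can detect impairment is a question of sensitivity and specificity. Kappa answers a different one. It treats the 6CIT and the MoCA as interchangeable raters, and it corrects for chance using the margins of the table. It therefore depends on how many people are positive as well as on how well the test performs.

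Here the share of positives is partly a design choice. If prevalence rises with age and half the sample is aged 70 or over, the sample holds more positives than the older-prisoner population does. The same test would then show a different kappa in the study from the one it would show in the prisons meant to use it. If kappa and sensitivity point in different directions, the text as written gives the suitability conclusion to kappa.

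**Working it through.** **The plan's own figure.** The protocol states no kappa value. Its relevant figure is the planning prevalence of 7%, with ±2 points at 95% confidence and a finite correction within each sex. Without the correction, n₀ = 1.96² × 0.07 × 0.93 / 0.02² = 625.2. With n = n₀ / (1 + (n₀ − 1)/N) and the 2014 counts in section 3:

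- men, N = 11,980: 594, against 591 stated;
- women, N = 437: 257, against 269 stated.

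The total is about 851, against 860. The population used for the correction is not stated, so the difference for women shows no error, and nothing below depends on it.

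**Formula.** With prevalence p, sensitivity Se and specificity Sp:

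- observed agreement Po = p·Se + (1 − p)·Sp
- share positive on the 6CIT q = p·Se + (1 − p)(1 − Sp)
- chance agreement Pe = p·q + (1 − p)(1 − q)
- kappa = (Po − Pe)/(1 − Pe)

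The documents give no sensitivity or specificity for the 6CIT, so all such values below are assumptions.

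**Step 1: one test, different prevalence (Se 0.80, Sp 0.90).**

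| p | Po | q | Pe | kappa |
|---|---|---|---|---|
| 7% | 0.893 | 0.149 | 0.802 | 0.46 |
| 15% | 0.885 | 0.205 | 0.707 | 0.61 |
| 30% | 0.870 | 0.310 | 0.576 | 0.69 |

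Accuracy is identical in every row.

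**Step 2: how far the age target departs from the population.** From section 3, men over 60 are 3,720 of 11,980 over 50 (31%), and women over 60 are 96 of 437 (22%). The share aged 70 or over must be smaller than that, against a target of 50%. The documents do not give the 70+ share or the prevalence by age band. Assume prevalence 5% at 50–69 and 20% at 70+, with the same test:

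- 70+ share 10%: p = 0.9 × 0.05 + 0.1 × 0.20 = 6.5%, kappa 0.44;
- 70+ share 31% (the ceiling for men): p = 0.69 × 0.05 + 0.31 × 0.20 = 9.65%, kappa 0.53;
- 70+ share 50% (the target): p = 12.5%, kappa 0.58.

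With other assumed prevalences, moving the 70+ share from 10% to 50% takes kappa from 0.43 to 0.53 (5% and 15%) or from 0.50 to 0.67 (5% and 40%).

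**Step 3: ranking of two rules.**

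| p | Se 0.50, Sp 0.98 | Se 0.80, Sp 0.90 |
|---|---|---|
| 7% | 0.538 | 0.460 |
| 10% | 0.560 | 0.534 |
| 12% | 0.566 | 0.569 |
| 15% | 0.571 | 0.608 |
| 30% | 0.551 | 0.693 |

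At 7%, kappa prefers the rule that misses 35 of 70 cases per 1,000 over the one that misses 14. From about 12% upward it prefers the more sensitive rule. At higher prevalence the less sensitive rule can still come out ahead, but only if the sensitive one has lower specificity: at 20%, a rule with Se 0.80 ranks below Se 0.50, Sp 0.98 only when its specificity is under 85.3%.

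**The case against.** The strongest reply is that the accuracy measures are already in the plan. The false negative rate is the missed-case figure, and a 6CIT that missed half the cases would be reported with a sensitivity of 50%. The paragraph opens with a detection aim, and nothing in it forbids using the accuracy estimates when suitability is judged. This stands in part. The measures are not missing; what is wrong is that the sentence drawing the conclusion follows kappa and weighted kappa and precedes the accuracy estimates, which it does not mention.

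A reader might infer more: that the study will choose a 6CIT cut-off by maximising kappa and so adopt a rule that misses half the impaired prisoners. The documents do not support that. They state no kappa cut-off and no rule for choosing a threshold, and the phrase about recognised levels can equally mean levels of impairment. The ranking in Step 3 rests on assumed values. The age target also pushes prevalence up, which weakens the reversal for that pair: in the 5% and 20% example the designed sample sits at 12.5%, just past the crossover. Moreover, the 7% comes from an earlier study using a different test, so the share positive on the MoCA may differ.

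It is also fair to say that layouts and supporting tables can be left to an analysis plan. Which measure carries the conclusion is stated in the protocol itself, and is open to comment here.

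**Conclusion.** The point holds at moderate severity. The protocol ties suitability for routine screening to agreement measures and leaves the planned accuracy measures unconnected to that conclusion. Kappa's dependence on prevalence is arithmetic and needs no particular 6CIT performance. Its size does depend on assumptions: for sensitivity 0.80 and specificity 0.90, kappa runs from 0.46 at 7% positive to 0.69 at 30%. In the 5% and 20% example, moving from a 70+ share of 10–31% to the 50% target raises it from 0.44–0.53 to 0.58. A verdict resting on kappa from this sample would therefore not carry over to older prisoners at large. That kappa may favour a less sensitive rule is a possibility at low prevalence, not a predicted outcome of this study.

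**What to change.** In section 4, Stage One, iii. Data Analysis:

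1. Move the suitability sentence so that it follows, and refers to, the sensitivity and specificity of the 6CIT against the MoCA, each with a 95% confidence interval.
2. Give positive and negative predictive values recalculated at the prevalence weighted to the real older-prisoner age mix. The Part Two questionnaire already collects the numbers and age distribution of prisoners aged 50 or over in each establishment, which could supply the weights.
3. Keep kappa and weighted kappa as a secondary description of agreement, and drop the statement that they establish suitability.

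The accuracy figures come from the 2×2 table already planned. Recruitment, sample size and data collection do not change. The cost is a few reworded sentences and one small extra table.

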This battery of tests will establish the broader needs of each older prisoner, including social support, daily living skills, co-morbidity and risk. Descriptive statistics will be produced. This information will inform the case vignettes in part 4; the analytical approach that we will use is outlined in detail in part 4 (please see 'stage 1: User profiling').

c. Stage Three – Prevalence study

Estimates will be calculated for current and for projecting future prevalence. We will generate a matrix of future prevalence estimates according to various hypothetical projected scenarios of overall prison population growth and of rising numbers of older prisoners in both absolute and proportional terms. If we have sufficient power in our final sample, we will produce age-standardised prevalence ratios and age-specific prevalence estimates, to allow comparison with community-based samples (e.g. Matthews et al, 2013). These estimates will be of intrinsic interest and value, and we will also use them to inform part 4, stage 4.

5. Study Part Two

Part two of the study will utilise a questionnaire to ascertain what health and social care services currently exist to identify and provide care for older prisoners with cognitive impairment and dementia in prisons, including how well multi-agency services are integrated. In addition, the questionnaire will explore levels of staff competency and confidence in this area, including identifying gaps in training and a detailed section on how any required training may best be delivered.

i. Sample

In part two of the study, a questionnaire will be issued to the governors and healthcare managers of all prisons housing adults, men and women, in England and Wales (n = 109). An up-to-date list of names and contact details of all health care managers will be obtained from the Offender Health Division at NHS England and cross-checked against records held by regional offender health leads. The questionnaire will be piloted in prisons in the North West of England before wider distribution. If any changes are made following the pilot, new or different questions only will be sent to the pilot prisons.

ii. Procedure

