The resources needed to provide the elements of each care pathway validated in stage 3 will be identified by the panel of experts and the annual cost of providing each care pathway will then be estimated by applying the unit costs in criminal justice produced by the Personal Social Services Research Unit to the resources identified (Brookes et al., 2013). These costs estimates will then be combined with the matrix of prevalence estimates produced in part 1 stage 3 to perform a budget impact analysis (BIA) of the costs of implementing the recommended care packages nationally. The various prevalence scenarios produced will be used to present a range of cost estimates, following the ISPOR task force principles of good practice for BIA (Mauskopf et al., 2007, Sullivan et al., 2014). Finally, the service provision data from the care-planning exercise will be entered into an excelbased cost-modelling template developed by the research team, to enable each prison site/commissioner to estimate their own projected costs given their populations.

e. Stage Five: Development of Training materials for prison based health and social care staff and prison officers

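### Age-specific prevalence is conditional on undefined power, although the sample over-represents ages 70+ and nothing weights it back, so projections and costs may use an inflated rate

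*Protocol*

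**What the plan says.** Protocol section 4.a.i (Sample, Sampling Procedure) stratifies by age, calling it "an important variable when investigating cognitive impairment, as prevalence doubles with every increase of five years". It aims for equal halves aged 50-69 and 70+, for men and for women. The target is 860 prisoners, "including 269 women and 591 men", sized within each sex for a prevalence of 7% with 95% limits of 5% and 9%.

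Section 4.a.iii (Data Analysis) plans percentages with 95% confidence intervals. It mentions no weighting.

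Section 4.c (Stage Three – Prevalence study) builds a matrix of future prevalence from "various hypothetical projected scenarios of overall prison population growth and of rising numbers of older prisoners in both absolute and proportional terms". The age breakdown follows as a conditional item: "If we have sufficient power in our final sample, we will produce age-standardised prevalence ratios and age-specific prevalence estimates". Its stated purpose is comparison with community samples, and the section adds that the estimates will inform the costing.

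Section 7.d (Stage Four: Cost projection) combines unit costs with that matrix: "The various prevalence scenarios produced will be used to present a range of cost estimates".

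Section 3 (Background) gives the 2014 population: 11,980 men over 50, of whom 3,720 were over 60, and 437 women over 50, of whom 96 were over 60.

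**The concern.** A sample that is half aged 70+ does not have the age mix of the older prison population. That is a legitimate design choice, since it buys information where impairment is most common. It obliges the analysis to work by age band or to weight back. The protocol makes the first optional and does not mention the second.

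The condition itself is poorly chosen. No test is planned on these estimates, so power has no defined meaning here. The relevant quantity is interval width, which can be worked out in advance for any cell size.

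If the condition is judged not to be met, what remains is a raw percentage from an age-skewed sample. Applied to counts of older prisoners, it would inflate the current case count, every cell of the projection matrix, and every cost proportional to cases. Prevalence and budget impact are both stated outputs for service planning.

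**Working it through.** **Reproducing the planned sample size.** Single-proportion precision: n0 = 1.96² × 0.07 × 0.93 / 0.02² = 625.2. Finite population correction: n = n0 / (1 + (n0 − 1)/N).

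- Men, N = 11,980: 594.3, so 595 against the stated 591. The half-width at 591 is 2.01 points.
- Women, N = 437: 257.5, so 258 against the stated 269. The half-width at 269 is 1.89 points, so the stated precision is met. The figure 269 would need N of about 471; the protocol does not say which N it used.

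The total of 853 is close to 860. The calculation assumes simple random sampling within each sex and makes no allowance for the age split.

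**Ceiling on the 70+ share.** The protocol gives no 70+ count, so the over-60 share is an upper bound: 3,720/11,980 = 31% for men and 96/437 = 22% for women. The sample target is 50%.

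**Bias of the unweighted rate.** Let p be prevalence at 50-69, kp prevalence at 70+, and w the population share aged 70+. The 50/50 sample gives p(1 + k)/2; the population value is p(1 + w(k − 1)). The overstatement is therefore

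R = [(1 + k)/2] / [1 + w(k − 1)].

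Neither k nor w is in the protocol. I assume k = 4 to 8 (two to three doublings, given the cited doubling every five years) and w = 5% to 20%.

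| w | k = 4 | k = 8 |
|---|---|---|
| 5% | 2.5/1.15 = 2.17 | 4.5/1.35 = 3.33 |
| 10% | 2.5/1.30 = 1.92 | 4.5/1.70 = 2.65 |
| 20% | 2.5/1.60 = 1.56 | 4.5/2.40 = 1.88 |
| 31% (male ceiling) | 2.5/1.93 = 1.30 | 4.5/3.17 = 1.42 |

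A shallower gradient, k = 2, gives 1.43 at w = 5% and 1.25 at w = 20%.

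**Women.** Half of 269 is about 135, but only 96 women were over 60 in 2014. On those figures the female 70+ target cannot be filled, so the table describes men, who are 11,980/12,417 = 96.5% of the population. Sex needs weighting too if the sexes are pooled: women are 269/860 = 31% of the sample and 437/12,417 = 3.5% of the population.

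**Would weighting cost too much precision?** For men, with about 295.5 per stratum, the variance is (1 − w)²p₁(1 − p₁)/295.5 + w²p₂(1 − p₂)/295.5, where p₁ and p₂ are prevalence at 50-69 and 70+. With w of 10% or 20% and (p₁, p₂) of (3.5%, 14%) or (5%, 20%), the half-width of the weighted estimate is 1.9 to 2.3 points, close to the planned 2. Single-stratum half-widths at 7% are 2.9 points for men and 4.3 for women. None of these allows for clustering by prison.

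**Sampling error on the counts.** Applying 7% (5% to 9%) to 11,980 + 437 = 12,417 prisoners gives 869 cases (621 to 1,118). That is 2/7, or ±29%, before any growth scenario.

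**The case against.** The best defence is that the condition is prudent. The final age mix is uncertain, recruitment will be reviewed after the first quarter, the female 70+ cell cannot be filled as planned, and the cited community comparator starts at 65, which cuts across the 50-69 stratum. Age-specific estimates are already meant to reach the costing, and the Part Two questionnaire (section 5.ii) collects the age distribution of prisoners aged 50+ at each establishment. A statistical analysis plan, not seen here, could add weighting.

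Much of this stands as a reason to pool small cells. It does not justify making the whole age breakdown optional, because weighting does not require every band to be precise. The condition is written into the protocol, with no fallback.

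A reader might infer more than the documents support:

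- **That a constant rate will understate future cases as prisoners age.** The over-60 share of both sexes combined was 1,680/5,477 = 30.7% in 2004 and 3,816/12,417 = 30.7% in 2014. The bias shown here comes from the sample's age mix and runs upward.
- **That the community comparison will be confounded by age.** The age-adjusted estimates are the stated means of comparison; no crude comparison is promised if they are dropped.
- **That precision is ample for every age band.** The acceptable half-widths apply to men in two strata and ignore clustering.
- **That a single rate will be used throughout.** The sample is sized within each sex, so sex-specific rates are available, although Stage Three does not require them.
- **That sampling error is excluded from the costs.** Intervals for prevalence are planned, and section 7.d commits to published budget-impact principles. The text does not say the intervals are carried forward; it does not rule it out.

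**Conclusion.** The point holds. The protocol over-represents the 70+ group by design, makes the age-specific analysis conditional on an undefined and unsuitable criterion, and provides no weighting to the population. If the condition fails, the plan as written leaves a rate biased upward by about 1.6- to 3.3-fold under the assumed shares and gradients, and by 1.3- to 1.4-fold at the largest 70+ share the male counts allow. These factors assume that the 50/50 split is achieved and that the unweighted rate is used. They apply chiefly to men; a sample that falls short of the 70+ target would be less biased.

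The sampling-error point is secondary. It rests partly on what the protocol leaves unsaid, but at the stated precision it amounts to ±29% on cases.

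**What to change.** In section 4.c, delete the power condition and state that:

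1. Prevalence with a 95% interval is always reported by sex and age band, with bands pooled below a stated minimum cell size. The female 70+ target is reconciled with the counts in section 3.
2. Overall prevalence is weighted to the age and sex distribution of the prison population aged 50+, for example using the counts from the Part Two questionnaire.
3. The projection matrix is built as age-band rate times projected age-band count.

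In section 7.d, as a cheap addition, run each budget-impact scenario at the point estimate and at both 95% limits of prevalence.

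The cost is analysis wording and some extra spreadsheet columns; no new data collection is needed if the questionnaire returns are adequate. The downside is that some age-specific intervals and cost ranges will be visibly wide, more so once clustering by prison is allowed for.
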